9.4.2.2. Supplementary Estimands

Three supplementary Estimands are defined to support the primary objective.

The first supplementary Estimand is defined in the same way as the main Estimand, except the assessment time frame for patients achieving SVR will be 24 weeks after the actual end of treatment. Therefore, the strategy for intercurrent events of treatment discontinuation will be while-on-treatment. This supplementary estimand supporting the primary objective in participants with CHB on stable NA therapy in each treatment arm is the percentage of participants that achieve SVR (HBsAg <LLOQ and HBV DNA <LLOQ) for 24 weeks after the actual end of sequential treatment in the absence of rescue medication, regardless of ineligibility to receive PegIFN, discontinuation of, interruption in or non-adherence to GSK3228836 and PegIFN, had they not been affected by wide disruptive events.

The second supplementary Estimand is to understand the relationship between the PegIFN duration and achieving SVR for 24 weeks after the actual end of treatment, defined as:

- Population: Participants with CHB on stable NA therapy
- Treatment: 300 mg GSK3228836 for 12 or 24 weeks followed by up to 24 weeks of PegIFN therapy while on stable NA therapy
- Variable: The relationship between SVR for 24 weeks after actual end of treatment and of PegIFN received by participants before completion or discontinuation of each treatment
- Intercurrent Events:
 - Discontinuation and delayed start of PegIFN will be accounted to reflect the actual duration from the first to the last dose of PegIFN received (while-on-treatment strategy).
 - Interruption in and other non-adherence to PegIFN will be ignored (treatment policy strategy).
 - Discontinuation of, interruption in and non-adherence to GSK3228836 will be ignored (treatment policy strategy).
 - Use of rescue medication (composite strategy).
 - Wide disruptive events (such as COVID-19 pandemic) leading to discontinuation and delayed start of PegIFN will be handled with while-on-treatment strategy; wide disruptive events leading to interruption in and other non-adherence to PegIFN will be ignored (treatment policy strategy); wide disruptive events leading to discontinuation of, interruption in, and non-adherence to GSK3228836 will be ignored (treatment policy strategy).
- Population Summary: The percentage of participants achieving SVR for 24 weeks after the actual end of treatment by PegIFN treatment duration categorical grouping (groupings to be defined in the RAP) in each treatment arm.

The second supplementary Estimand (supporting the primary objective in participants with CHB on stable NA therapy) is percentage of participants achieving SVR for 24 weeks after the actual end of treatment by PegIFN treatment duration categorical grouping in each treatment arm, taking into account discontinuation and delayed start of PegIFN, regardless of interruption in and other non-adherence to PegIFN, regardless of discontinuation of, interruption in and non-adherence to GSK3228836. The PegIFN treatment duration will support interpretation of the percentage of participants achieving SVR for 24 weeks after the actual end of treatment, especially if participants discontinue from PegIFN early or delay start of PegIFN due to ineligibility.

The third supplementary Estimand is defined in the same way as the main Estimand, except the strategy for intercurrent events of PegIFN ineligibility for more than 12 weeks (i.e. can no longer receive at least 12 weeks of PegIFN treatment) and/or missing at least 12 doses

of PegIFN will be principal stratum. This supplementary Estimand supporting the primary objective is the percentage of participants in each treatment arm that achieve SVR (HBsAg <LLOQ and HBV DNA <LLOQ) for 24 weeks after the planned end of sequential treatment in participants with CHB on stable NA therapy and receiving at least 12 doses of PegIFN, in the absence of rescue medication, regardless of discontinuation of, interruptions in or non-adherence to GSK3228836 had they not been affected by wide disruptive events.

9.4.2.3. Handling of Withdrawal from Study and Missing HBsAg and HBV DNA Data

Two approaches will be used to determine a participant's response when HBsAg and HBV DNA data are missing from visits required to derive the primary Estimand.

1) For participants where wide disruptive events (such as COVID-19 pandemic) prevent assessment of the primary outcome, SVR will be imputed using all available data for participants for whom SVR can be assessed. For other participants where SVR in the absence of rescue medication cannot be ascertained due to missing data (withdrawal from the study or missing due to other reasons, but not due to a wide disruptive event), the participant will be assumed not to have achieved SVR (non-responder imputation).

2) For the main estimand supporting the primary objective, a sensitivity analysis will be performed using the Bayesian model described in Section 9.4.2.4 assuming missing at random whereby a participant's response will be imputed using all available data (on and off treatment values) for participants who completed the study.

9.4.2.4. Primary Analyses

The primary assessments of interest are the point estimate of sustained virologic RR and 95% credible intervals; in addition, posterior probabilities that the true virologic RR in each treatment arm is greater than a range of values will be provided.

A Bayesian hierarchical model will be used to estimate the posterior probability of sustained virologic RR incorporating the baseline stratification factors [Jones, 2011]. Main effects for each of the 2 strata will be included as independent parameters in the model denoted γ_k ($k = 1, 2$); Interactions between the 2 levels of stratification factors are anticipated to be small, and so will be modelled as exchangeable random effects (ψ_g) centred on zero to enable borrowing of information about the RR across strata.

$$\theta_g = \tau + \gamma_1 I_{\{B1+\}} + \gamma_2 I_{\{B2+\}} + \psi_g$$

$$\tau \sim \text{Normal}(0, 10^6)$$

$$\gamma_k \sim \text{Normal}(0, 10^6), k = 1, 2$$

$$\psi_g \sim \text{Normal}(0, \omega^2), g = 1, 2, 3, 4$$

$$\omega \sim \text{Half - Normal}(1)$$

Where θ_g is defined as the log odds of treatment response, index $g=1, 2, 3,$ and 4 on the random effect ψ refers to each of the 4 possible combinations of strata levels. The parameter $\tau + \psi_1$ represents the treatment effect in reference stratum (HBsAg ≤ 3 log IU/mL and Negative HBeAg), while g denotes a random stratum effect in group g .

The four stratum and representation of the two baseline stratification factors B_1 and B_2 in the model are shown in [Table 15](#).

Table 15 Baseline Stratification Factors for Four Stratum

Stratum	B ₁ : HBsAg	B ₂ : HBeAg
1: HBsAg < 3 log IU/mL and Negative HBeAg	B ₁₋ (≤ 3 log IU/mL)	B ₂₋ (Negative)
2: HBsAg ≥ 3 log IU/mL and Negative HBeAg	B ₁₊ (> 3 log IU/mL)	B ₂₋ (Negative)
3: HBsAg < 3 log IU/mL and Positive HBeAg	B ₁₋ (≤ 3 log IU/mL)	B ₂₊ (Positive)
4: HBsAg ≥ 3 log IU/mL and Positive HBeAg	B ₁₊ (> 3 log IU/mL)	B ₂₊ (Positive)

The point estimates of sustained virologic RR in each treatment arms with 95% credible intervals will be calculated. Handling of withdrawal from study and missing HBsAg and HBV DNA data is described in [Section 9.4.2.3](#).

Posterior probability of sustained virologic RR exceeding a range of clinically meaningful RRs will be generated using the model specified.

9.4.3. Secondary Endpoints

9.4.3.1. Secondary Estimands

Three groups of estimands are defined for the secondary efficacy objectives. Categorical definitions for secondary analyses will be provided in the RAP.

1. Estimands supporting secondary objective of assessing the efficacy of GSK3228836 and PegIFN sequential therapy on biomarkers and virus specific antibody responses are defined as follows:
 - Population: Participants with CHB on stable NA therapy; For the time to ALT normalisation variable, population will be aforementioned participants with baseline ALT $> \text{ULN}$.
 - Treatment: 300 mg GSK3228836 for 12 or 24 weeks followed by up to 24 weeks of PegIFN therapy while on stable NA therapy
 - Intercurrent Events: Discontinuation of, interruption in, and non-adherence to GSK3228836 and PegIFN will be ignored (treatment policy). PegIFN ineligibility will be ignored (treatment policy); Rescue medication will be ignored (treatment policy), except for ALT normalisation which can only be achieved in the absence

- of rescue medication; Wide disruptive events (such as COVID-19 pandemic) leading to discontinuation of, interruption in, and non-adherence to GSK3228836 and PegIFN will be ignored (treatment policy strategy).
- Categorical Variables:
 - Achieving HBsAg <LLOQ and HBV DNA <LLOQ at two time points: (1) the planned end of treatment and (2) at the end of 24 weeks follow-up
 - Categorical changes from baseline in HBsAg (e.g., <0.5, ≥0.5, ≥1, ≥1.5, ≥3 log₁₀ IU/mL).
 - ALT normalisation (ALT ≤ ULN) over time in absence of rescue medication in participants with baseline ALT > ULN
 - HBe antibody (anti-HBeAg) levels
 - Population summary of Categorical Variables: percentage of participants in each category for each treatment arm
 - Continuous Variables:
 - Actual values and change from baseline over time of HBsAg, HBV DNA, and HBeAg levels
 - Actual values and change from baseline over time for HBs antibody (anti-HBsAg) levels over time
 - Actual values and change from baseline over time for ALT.
 - Population summary of Continuous Variables: mean values and mean changes from baseline of each variable for participants in each treatment arm
 - Time to Event Variable:
 - Time to ALT normalisation in absence of rescue medication in participants with baseline ALT > ULN
 - Population summary of Time to Event Variable: Turnbull's estimator for non-parametric estimation of Time to ALT normalisation in each treatment arm

The estimands supporting this objective are the population summary for each variable in each treatment arm in the population regardless of discontinuation of, interruption in, or non-adherence to planned treatment, and regardless of rescue medication (except for ALT normalisation which can only be achieved in the absence of rescue medication) or PegIFN ineligibility.

Missing data for variables defined above will be ignored, only available data will be summarised. Further details will be provided in the report and analysis plan (RAP).

2. Estimands supporting secondary objective of investigating the durability of virological response after sequential therapy with 12 weeks of GSK3228836 followed by up to 24 weeks of PegIFN in participants with CHB on stable NA therapy for up to 36 weeks

off treatment are defined the same as the above secondary estimand, focusing on the timepoints following the 24 weeks off-treatment period.

3. Estimands supporting secondary objective of comparing efficacy between treatment arms of 12 and 24 weeks of GSK3228836 followed by up to 24 weeks of PegIFN are defined as follows:
- Population: Participants with CHB on stable NA therapy
 - Treatment: 300 mg GSK3228836 for 12 or 24 weeks followed by up to 24 weeks of PegIFN therapy while on stable NA therapy. One treatment comparison between Arms 1 and 2 up to 24 weeks off-treatment
 - Categorical Variables:
 - Achieving SVR (HBsAg <LLOQ and HBV DNA <LLOQ) at the planned end of sequential treatment and over the 24 weeks follow-up.
 - Population Summary of Categorical Variables: difference in percentage of participants who achieve SVR between treatment arms.
 - Intercurrent Events: Discontinuation of, interruption in, and non-adherence to GSK3228836 and PegIFN will be ignored (treatment policy). PegIFN ineligibility will be ignored (treatment policy); Participants who have used rescue medication will be counted as non-responders (composite strategy); Wide disruptive events (such as COVID-19 pandemic) leading to discontinuation of, interruption in, and non-adherence to GSK3228836 and PegIFN will be handled assuming they had not happened (hypothetical strategy).

The estimands supporting this objective in participants with CHB on stable NA therapy for the treatment comparison is the difference between treatment arms 1 and 2 in the proportion of participants that achieve SVR for 24 weeks after the planned end of sequential treatment, in the absence of rescue medication, regardless of ineligibility to receive PegIFN, regardless of discontinuation of, interruptions in or non-adherence to GSK3228836 and PegIFN, had they not been affected by wide disruptive events.

9.4.3.2. Handling of withdrawal from study and missing data for secondary endpoints

9.4.3.2.1. Comparison of efficacy between treatment arms

Two approaches will be used to determine a participant's response when HBsAg and HBV DNA data are missing from visits required to derive the secondary estimand of comparing efficacy between treatment of 12 and 24 weeks of GSK3228836 followed by up to 24 weeks of PegIFN

1) For participants where wide disruptive events (such as COVID-19 pandemic) prevent assessment of the HBsAg and HBV DNA required to derive SVR, SVR will be imputed using all available data for participants for whom SVR can be assessed. For other participants where SVR in the absence of rescue medication cannot be ascertained due to missing data (withdrawal from the study or missing due to other reasons, but not due to a

wide disruptive event), the participant will be assumed not to have achieved SVR (non-responder imputation).

2) For the estimand supporting the objective of comparing efficacy between treatment arms, a sensitivity analysis will be performed using the Bayesian model described in Section 9.4.3.3 assuming missing at random whereby a participant's response will be imputed using all available data (on and off treatment values) for participants who completed the study.

9.4.3.2.2. Other secondary endpoints

Other than the HBsAg and HBV DNA data supporting the secondary objective of comparing efficacy between treatment arms, missing data for variables defined in any other secondary or exploratory estimand will be ignored, assuming missing completely at random.

9.4.3.3. Secondary Efficacy Analyses

The secondary efficacy comparison of interest is the difference in sustained virologic RR for 24 weeks after the planned end of sequential treatment between treatment arms:

- Arm 1 vs. Arm 2 in percentage of participants achieving SVR for 24 weeks after the planned end of sequential treatment, without use of any rescue medication.

The model in Section 9.4.2.4 will be used to separately estimate the log odds of response for each treatment arm. Comparisons between the treatment arms will be conducted by taking difference of log odds. The point estimates of differences in sustained virologic RR with 95% credible intervals will be calculated for the treatment comparisons described in the estimands. Handling of withdrawal from study and missing HBsAg and HBV DNA data is described in Section 9.4.3.2. Details of the model will be included in the RAP.

9.4.4. Safety Endpoints

All safety analyses will be based on the Safety Population.

Exposure to study medication, measured by the number of injections and proportion of planned number of injections of study drug, will be summarised by treatment arm.

The proportion of participants reporting AEs will be tabulated for each treatment arm. The following summaries of AEs will be provided:

- Incidence and severity of All AEs;
- Incidence and severity of treatment related AEs;
- Incidence and severity of AEs leading to withdrawal from study;
- Incidence of serious AEs (SAEs).

Laboratory data, vital signs and ECG data (absolute values and change from Baseline) will be summarised by visit and treatment arm. In addition, the maximum postbaseline toxicity grade (based on DAIDS categories) will be tabulated by treatment arm.

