
Endocrine disorders:
 
Thyroid function abnormalities or worsening of pre-existing thyroid disorders
 
Hypoglycaemia/Hyperglycaemia/Diabetes Mellitus
	
Thyroid function abnormalities or worsening of pre-existing thyroid disorders have been reported with the use of alfa interferons, including PegIFN.
 
Hypoglycaemia, hyperglycaemia and diabetes mellitus have been observed with PegIFN.
	
Participants with uncontrolled thyroid function are excluded from this study. Thyroid function tests will be monitored as per the SOA. Abnormalities of thyroid function should be managed according to local guidance. If thyroid function cannot be adequately managed PegIFN treatment should be discontinued.
 
Participants with uncontrolled diabetes are excluded from this study. Blood glucose will be monitored throughout the study.

Potential Risk of Clinical Significance	Summary of Data/Rationale for Risk	Mitigation Strategy
		Abnormalities of blood glucose should be managed according to local guidance. If blood glucose cannot be adequately managed PegIFN treatment should be discontinued.
Cardiovascular disorders: Hypertension, supraventricular arrhythmias, congestive heart failure, chest pain and myocardial infarction	These have been associated with alfa interferon therapies, including PegIFN.	
Patients with significant/unstable cardiac disease are excluded from the study.
 
Participants will undergo an electrocardiogram (ECG) at screening and prior to PegIFN treatment.
 
If there is any deterioration of cardiovascular status, therapy should be suspended or discontinued.

Retinopathy including retinal haemorrhages, cotton wool spots, papilloedema, optic neuropathy and retinal artery or vein obstruction which may result in loss of vision	These have been reported in rare instances with PegIFN.	
All participants will have a baseline eye examination.
 
Any participant complaining of a change in vision or a new visual disturbance will have an urgent eye examination and PegIFN should be discontinued.

Fever/Infections	Serious infections (bacterial, viral, fungal) and sepsis have been reported during treatment with alfa interferons including PegIFN.	Appropriate anti-infective therapy should be started immediately, and discontinuation of PegIFN should be considered

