8.2.3. Vital Signs

Temperature, pulse rate, respiratory rate, and blood pressure will be assessed.

Blood pressure and pulse measurements will be assessed with a completely automated device. Manual techniques will be used only if an automated device is not available.

Blood pressure and pulse measurements should be preceded by at least 5 minutes of rest for the participant in a quiet setting without distractions (e.g., television, cell phones).

Vital signs will be measured after 5 minutes rest and will include temperature, systolic and diastolic blood pressure, and pulse and respiratory rate.

If assessments are scheduled for the same nominal time, then 12-lead ECG and vital signs must be completed prior to blood collection. The order of conducting the 12-lead ECG and vital sign measurements is flexible but should allow the blood collection to occur at the exact nominal time.

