4.5.3. Additional Safety Assessments

4.5.3.1. Laboratory Data

Only central lab data will be used for summary analyses and figures; local lab data will be included in listings, as appropriate.

If normal LAB ranges are collected and there are duplicate LAB records at the same date/timepoint, the “worst-case” value will be selected. Specifically:

- For LAB result > Lower Normal range, select Maximum of Lab result (AVAL).
- For LAB result \leq Lower Normal range, select minimum of Lab result (AVAL).

For virology LAB parameters, if time information is missing from collection and from the test performed, the maximum lab value should be selected. If first run has values outside acceptance criteria, and the sample was re-run, the latest LAB result should be selected by the vendor.

Summary statistics for changes from baseline for each numeric parameter at each visit will be presented, separately for all clinical chemistry parameters, all haematology parameters, and all urinalysis parameters.

For immunology parameters, summary statistics for actual value and change from baseline data for each parameter at each visit will be presented, separately for all numeric parameters. Listings will also be created.

For categorical immunology parameters c-ANCA and p-ANCA, summary table of baseline Negative to post-baseline Positive, baseline value no change, and baseline Positive to post-baseline Negative will be created. Listing will be created as well.

For coagulation parameters prothrombin international normalised ratio (INR), prothrombin time (PT_{test}) and activated partial thromboplastin time (aPTT), summary statistics for actual at each visit will be presented. Listing will be created as well.

Shift tables for laboratory parameters showing baseline toxicity versus maximum post-baseline (on-treatment and off-treatment periods combined) toxicity for each grade (Grade1, Grade 2, etc.) for chemistry and haematology parameters will be provided.

Increase to Grade 3 or higher lab abnormalities for platelets, ALT, aspartate aminotransferase (AST), INR, total bilirubin, serum creatinine, eGFR, albumin to creatinine ratio (ACR) will be summarized.

Laboratory values outside of normal range will be summarized and listed.

Grading categories for laboratory tests are determined using the DAIDS grading system Version 2.1 [[National Institute of Allergy and Infectious Diseases. Division of AIDS, 2017](#)].

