4.5.3.2. Vital Signs

Summaries of grade increase in temperature, systolic blood pressure (SBP) and diastolic blood pressure (DBP) will be provided separately. These summaries will display the number and percentage of participants with any grade increase, increase to Grade 2, increase to Grade 3 and increase to Grade 4 (for temperature only), for worst case post-

baseline only. The grade definition for non-axillary temperature is: Grade 1 (38.0°C – <38.6°C), Grade 2 (38.6°C – <39.3°C), Grade 3 (39.3°C – <40.0°C), Grade 4 (\geq 40.0°C). The grade definition for SBP is: Grade 1 (140-159), Grade 2 (160-179), Grade 3 (\geq 180). The grade definition for DBP is: Grade 1 (90-99), Grade 2 (100-109), Grade 3 (\geq 110). The summaries will be produced for worst case post baseline only.

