4.8. Changes to Protocol Defined Analyses

Changes from the originally planned statistical analysis specified in the protocol are detailed in Table 10

Table 10 Changes to Protocol Defined Analyses

Protocol Defined Analysis	SAP Defined Analysis	Rationale for Changes
Section 3 Objectives and Estimands and where applicable throughout	Updated text defining the population for the efficacy objectives align with the definition of intent-to-treat (ITT) population which will be used in efficacy analyses and is defined as all randomized participants.	To align with Study 209668 (B-Clear).
Section 3 Objectives and Estimands and Section 9.4.3.1 Secondary Estimands	Secondary Efficacy Endpoints: moved HBe antibody (anti-HBeAg) levels from a continuous variable to a categorical variable.	Correction.
NA – addition	SAP Section 4.2.5.1: Additional estimand to assess efficacy using a modified definition of SVR	Rationale is based on B-clear study , i.e. there are possible subjects with single lab values that are aberrant in terms of the individual's overall trajectory of response. There is some evidence that the aberrant values have occurred because of an unresolvable error at the site/lab. As the issues cannot be resolved in the data, this analysis will be used to support the primary objective.
Section 9.5 Interim Analysis	Unplanned interim analysis added	Support of internal decisions for platform trial (Study 218309)

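### The SAP does not specify the by-visit vital-signs summary promised in the protocol, which leaves pulse and respiratory rate with no planned safety summary

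*Protocol*

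**What the plan says.** Protocol 8.2.3 lists what is measured: "Temperature, pulse rate, respiratory rate, and blood pressure will be assessed". Counting systolic and diastolic pressure separately, that is five measures.

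Protocol 9.4.4 sets the analysis: "Laboratory data, vital signs and ECG data (absolute values and change from Baseline) will be summarised by visit and treatment arm". The sentence after it reads: "In addition, the maximum postbaseline toxicity grade (based on DAIDS categories) will be tabulated by treatment arm". Grades therefore supplement the by-visit summary and do not replace it.

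SAP 4.5.3.2 is the only SAP section that defines vital-signs output for safety. It says "Summaries of grade increase in temperature, systolic blood pressure (SBP) and diastolic blood pressure (DBP) will be provided separately", and closes with "The summaries will be produced for worst case post baseline only". Grades start at 38.0°C for temperature, 140 for systolic and 90 for diastolic pressure. No grade is defined for a low value, and pulse and respiratory rate are not mentioned.

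For the other two data types in the same protocol sentence, the SAP keeps a by-visit summary. SAP 4.5.3.3 keeps values and changes for ECG. For chemistry, haematology and urinalysis, SAP 4.5.3.1 says "Summary statistics for changes from baseline for each numeric parameter at each visit will be presented".

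On departures from the protocol, SAP 4.8 says "Changes from the originally planned statistical analysis specified in the protocol are detailed in" Table 10.

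**The concern.** An explicit protocol commitment on safety analysis has been narrowed in the SAP without being declared.

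The protocol's risk table (2.3.1) names hypertension, supraventricular arrhythmia and congestive heart failure among the PegIFN risks. Its mitigation includes ECGs, but only before that drug starts: "Participants will undergo an electrocardiogram (ECG) at screening and prior to PegIFN treatment". During PegIFN and off-treatment follow-up, scheduled information on heart rate comes from the pulse reading taken with the vital signs, and the SAP plans no safety summary of it.

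If the SAP is followed as written, the study report would contain no planned descriptive display of a shift in pulse or respiratory rate in either arm, and none of a fall in blood pressure. A single worst value per participant also does not show when a change arose. In a sequential two-drug study, that timing helps to tell which drug it may belong to.

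**Working it through.** No formula applies; the check sets the sections side by side.

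**Step 1: parameters.**

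| Measure collected (Protocol 8.2.3) | By-visit value and change (Protocol 9.4.4) | By-visit value or change in SAP 4.5.3.2 | Grade table in SAP 4.5.3.2 | Can a low value show? |
|---|---|---|---|---|
| Temperature | Yes | No | Upward, worst case | No |
| Systolic pressure | Yes | No | Upward, worst case | No |
| Diastolic pressure | Yes | No | Upward, worst case | No |
| Pulse rate | Yes | No | None | No |
| Respiratory rate | Yes | No | None | No |

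A by-visit display is defined for 0 of 5 measures. A safety summary of any kind is defined for 3 of 5, in one direction only, which leaves 5 − 3 = 2 with none.

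**Step 2: what a grade increase can show.** A fall in systolic pressure can only lower the grade or leave it unchanged, so it never counts. A rise that stays below 140, or that stays inside one band such as 140 to 159, does not count either. The by-visit summary would reflect such changes at group level.

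**Step 3: ECG timing.** The protocol's Table 1 has an ECG at screening. Tables 2 and 3 have one near the end of GSK3228836 dosing (from Week 23 in Arm 1 and Week 11 in Arm 2), and their footnotes require it before PegIFN begins. Table 4 (PegIFN dosing), Table 5 (eligibility reassessment) and Table 7 (off-treatment follow-up and early termination) have no ECG row, while all three have a vital-signs row. The by-visit ECG summary in SAP 4.5.3.3 therefore has no scheduled data once PegIFN has started.

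**Step 4: was the change declared?** Table 10 in SAP 4.8 has four rows: the wording of the efficacy population, the move of anti-HBeAg to a categorical variable, the modified SVR estimand, and the unplanned interim analysis. None concerns vital signs.

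**Step 5: consistency within the SAP.** SAP 6.2.8, Table 19, assigns vital signs taken at early termination to named weeks in every phase. SAP 6.2.4 says which of several windowed values enters the summary statistics of observed values. Such rules serve a by-visit table, and SAP 4.5.3.2 defines none. This looks more like an omission than a decision to withdraw the analysis.

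**The case against.** The strongest reply is that the SAP section is incomplete rather than contradictory. SAP 4.1.1 gives default descriptive statistics for continuous data, and the windowing and selection rules in SAP 6.2.4 and 6.2.8 imply that a by-visit vital-signs table is expected. The SAP also leaves some output detail to an Output and Programming Specification, which is not among the documents and may list such a table. This stands as a reason not to assume that the display will not be produced. It does not remove the mismatch: SAP 4.5.3.2 states a positive rule that its summaries are worst case only, and a programmer following it would produce no such table.

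A reader might infer that pulse is never analysed. The documents do not support that. SAP 4.4.2.3 names vital signs generically among the PK-PD safety assessments, as data permit and under a separate plan. Protocol 10.3.1 allows vital-sign abnormalities judged clinically significant to be recorded as adverse events. Arrhythmia and heart failure have their own case report form page (Protocol 8.3.6 and 10.3.3), and SAP 4.5.2 tabulates adverse events by arm and by treatment period. These routes capture events and exploratory relationships, but not the by-visit, by-arm description promised in Protocol 9.4.4.

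It can also be said that the cited hypertension risk is an upward one, which the pressure grades do capture, and that Protocol Section 3 places safety among the exploratory objectives and describes it through laboratory measurements and adverse events. Both are fair and limit the weight of the point. Neither overrides the explicit text of 9.4.4.

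A reader might extend the criticism to laboratory data, because SAP 4.5.3.1 gives only changes by visit for chemistry and haematology. For ALT this is wrong: SAP 4.3.1.1 plans actual values over time. For the other tests, toxicity-grade shifts, out-of-range values and the stopping and dose-modification events are already summarised, so threshold crossings are not hidden.

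**Conclusion.** The point holds as a conflict between protocol and SAP on safety reporting. None of the five vital signs has the by-visit summary that Protocol 9.4.4 specifies, pulse and respiratory rate have no planned safety summary, decreases in blood pressure cannot be seen in the planned output, and SAP 4.8 does not record the change. The gap matters most for pulse, because no ECG is scheduled once PegIFN starts.

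The size is moderate. The primary and secondary efficacy analyses are unaffected, and clinically significant events are still reported as adverse events. What is missing is the description of group-level shifts over time. The conclusion assumes that SAP 4.5.3.2 is read as the complete list of vital-signs safety output. If the programming specification already lists the by-visit tables, the remaining defect is that the SAP does not say so.

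**What to change.** In SAP 4.5.3.2, add summaries of absolute value and change from baseline, by visit and treatment arm, for pulse rate, respiratory rate, systolic pressure, diastolic pressure and temperature. Keep the worst-case grade tables, since Protocol 9.4.4 asks for grades as well. If the sponsor intends the narrower output, record it with a reason in SAP 4.8, Table 10; that would settle the mismatch on paper but leave heart rate on PegIFN without a summary.

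As a minor alignment with Protocol 9.4.4, SAP 4.5.3.1 could also give absolute values by visit for the remaining chemistry and haematology tests.

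The cost is a few standard descriptive tables. The data are already collected, the windowing rules for early-termination visits already exist, and no new visit or assessment is needed.
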